9.4.8 Planned Interim Analyses

No interim analyses are planned.

9.4.9 Additional Sub-group Analyses

Selected analyses may be performed in subgroups. Details will be provided in the SAP.

9.4.10 Multiple Comparison/Multiplicity

A hierarchical testing procedure will be used to control the Type I error rate across the primary and key secondary endpoints. The primary endpoint will be tested at a significance level of 0.05 and if this test is significant, the key secondary endpoint will also be tested at a significance level of 0.05. If the primary endpoint test is not significant then the key secondary endpoint is also not significant.

Other secondary endpoints will be tested at a nominal significance level of 0.05 (2-sided).

9.4.11 Tabulation of Individual Response Data

Listings of the individual response data will be provided by measure and time point.

9.4.12 Exploratory Analyses

Additional exploratory analyses may be defined in the SAP.

9.5 Sample Size

A total sample size of 168 evaluable subjects was estimated to provide at least 80% power at a two-sided significance level of 0.05 assuming a mean change in HAMD-17 total score of -7.8 (SD=8.0) and -10 (SD=8) in Stage 1, and -2.8 (SD=6) and -6.0 (SD=6) in Stage 2 for the placebo and pimavanserin groups, respectively.

For the above calculation, the weight for each double-blind treatment stage is equal to 0.5 and it is assumed that approximately 70% of placebo subjects will be non-responders at the end of Stage 1.

Adjusting for a potential non-evaluable rate of up to 10%, approximately 188 subjects will be randomized into Stage 1 (47 to pimavanserin and 141 to placebo). It is anticipated that approximately 98 subjects will be randomized into Stage 2 (49 to pimavanserin and 49 to placebo).

9.6 Measures to Minimize Bias

9.6.1 Masking Procedures

This unmasked protocol version provides details of certain study design elements, procedures, and statistical methods that are not available in the masked version of the protocol.

This document is intended for use only by unmasked ACADIA or [REDACTED] personnel or their designated agents or for review only by IRBs, IECs, regulatory authorities, or any other entity considered suitable by ACADIA.

The information contained herein is UNMASKED and CONFIDENTIAL. Therefore, it must NOT be shared with or communicated to any individual at an investigational site or from site facing members of the clinical operations team of the CRO except with explicit and fully documented authorization from ACADIA.

Key elements revealed but that are masked in the masked protocol include:

- The 2-stage Sequential Parallel Comparison Design of the study and related details.
- The duration and timing of the efficacy period.
- Full definition of Stage 1 and Stage 2 baseline, admission and non-responder criteria and timepoints.
- Details of the statistical methodology that are specific to the Sequential Parallel Comparison Design

Investigators will receive the masked version of the clinical study protocol.

Investigators will be informed of the 10-week treatment period but will remain masked to the distinction between Stage 1 and Stage 2.

In order to maintain the masking of the re-randomization visit, Investigators will enter the HAMD-17 total score for the subject at every visit into Interactive Response Technology (IRT).

9.6.2 Randomization Procedures

9.6.2.1 Stage 1 Double-blind Treatment Period

Subjects who meet the criteria for study eligibility will continue to receive their SSRI/SNRI antidepressant at a stable dose for the duration of the study and will be randomly assigned (1:3) to pimavanserin 34 mg or placebo.

9.6.2.2 Stage 2 Double-blind Treatment Period

At the end of Stage 1 (Week 5), subjects initially randomized to placebo and who have met the predefined non-responder criteria (i.e., HAMD-17 total score at Week 5 >14 and percent-reduction from the Week 0 (Baseline) HAMD-17 total score of $<50\%$) are randomly assigned (1:1) to pimavanserin 34 mg or placebo. The determination of the subject's status and eligibility for randomization in the Stage 2 will be made in the double-blind manner via the IRT system. Subjects who do not meet criteria for randomization into Stage 2 will continue with the assigned treatment from Stage 1 for an additional 5 week period (until the end of the study double-blind treatment).

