1.3.1 Known Potential Risks

The Prescribing Information for NUPLAZID[®] (pimavanserin) tablets for oral use (ACADIA Pharmaceuticals Inc., 2017) indicates the following contraindication and includes the following Boxed Warnings:

- Contraindication: NUPLAZID is contraindicated in patients with a history of hypersensitivity reaction to pimavanserin or any of its components. Reactions have included rash, urticaria, tongue swelling, circumoral edema, and throat tightness.

- **Boxed Warnings:**
 - Increased mortality in elderly patients with dementia-related psychosis; elderly patients with dementia-related psychosis treated with antipsychotic drugs are at an increased risk of death
 - Not approved for the treatment of patients with dementia-related psychosis unrelated to the hallucinations and delusions associated with Parkinson's disease psychosis

The increased mortality in elderly patients is based on information regarding antipsychotic drugs generally, rather than on specific pimavanserin data. Antipsychotic drugs increase the all-cause risk of death in elderly patients with dementia-related psychosis. Analyses of 17 dementia-related psychosis placebo-controlled trials (modal duration of 10 weeks and largely in patients taking atypical antipsychotic drugs) revealed a risk of death in the drug-treated patients of between 1.6- to 1.7-times that in placebo-treated patients. Over the course of a typical 10-week controlled trial, the rate of death in drug-treated patients was about 4.5%, compared to a rate of about 2.6% in placebo-treated patients. Although the causes of death were varied, most of the deaths appeared to be either cardiovascular (e.g., heart failure, sudden death) or infectious (e.g., pneumonia) in nature.

The Warnings and Precautions section of the Prescribing Information for pimavanserin also includes QT interval prolongation. Pimavanserin prolongs the QT interval. The magnitude of effect in humans has been assessed in a thorough QT study with doses of pimavanserin ranging from 17 to 68 mg and in a Phase 3 Parkinson's Disease psychosis program with a clinical dose of 34 mg. An average prolongation of approximately 5-8 ms was observed.

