12. Has a positive test for an illicit drug or cannabis at Screening or Baseline. Subjects who test positive for a controlled substance and who have a valid prescription may be retested if they agree to abstain from the medication for the length of their participation in the study. The repeat test, and any other tests, must be negative for them to participate in the study.

13. Has a history of seizure disorder or of neuroleptic malignant syndrome/serotonin syndrome. Single, absence, or febrile seizures are not exclusionary.
14. Is experiencing hallucinations, delusions, or any psychotic symptomatology in the current MDE.
15. Has received new-onset psychotherapy or has had a change in the intensity of psychotherapy within the 8 weeks prior to Screening.
16. Has received electroconvulsive therapy (ECT) during the current MDE.
17. Has a known history of long QT syndrome or family history of sudden cardiac death.
18. Has a Screening or Baseline ECG with a QTcF >450 ms when the QRS duration is <120 ms or has a Screening or Baseline ECG with a QTcF >470 ms when the QRS duration is \geq 120 ms. (The ECG may be repeated once at Screening or Baseline in consultation with the Medical Monitor.)
19. Has a significant sensitivity or allergic reaction to pimavanserin or its excipients.
20. Has previously been randomized in any prior clinical study with pimavanserin, and/or has received any other investigational (either approved or unapproved) drug within 30 days or 5 half-lives (whichever is longer) prior to Screening.
21. Has participated in >2 clinical research trials utilizing an investigational product within the previous 2 years.
22. Is an employee of ACADIA Pharmaceuticals Inc. or is a family member of an employee of ACADIA Pharmaceuticals Inc.
23. Has a history of minimal or non-response to adjunctive antipsychotics, such as quetiapine or aripiprazole, for prior MDEs, as clinically assessed by the Investigator.
24. Has a history of myocardial infarction, unstable angina, acute coronary syndrome, or cerebrovascular accident (CVA) within the last 4 months. Has greater than NYHA Class 2 congestive heart failure or Class 2 angina pectoris, sustained ventricular tachycardia (VT), ventricular fibrillation, torsade de pointes, or syncope due to an arrhythmia.

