The Investigator (or designee) will determine whether a patient meets eligibility criteria and will collect the demographic and medical data permitting full characterization of subjects.

Table 2 Schedule of Assessments

Visit	Screening 1	Double-blind Treatment Period											~30-Day Follow-Up ^a
		Baseline 2	3	4	5	6	7	8	9	10	11	12	
	(Day -21 to -8)	Week 0	Week 1	Week 2	Week 3	Week 4	Week 5	Week 6	Week 7	Week 8	Week 9	Week 10/ET	
Visit window (days)			±3	±3	±3	±3	±3	±3	±3	±3	±3	±3	+7
Informed consent and if applicable, privacy forms	X												
Inclusion/exclusion criteria	X	X											
Medical history, medication history, and demographics	X												
Psychiatric history	X												
MGH ATRQ	X												
SAFER remote interview	X												
SCID-5-CT	X												
Physical examination	X	X					X					X	
Vital signs	X	X	X	X	X	X	X	X	X	X	X	X	X
Height and weight ^b	X	X	X	X	X	X	X	X	X	X	X	X	X
12-lead ECG ^c	X	X	X				X	X				X	
Clinical laboratory tests ^{d,e}	X	X					X					X	
Pregnancy test ^f	X	X					X					X	
PK blood draws ^g	X	X	X		X		X	X		X		X	
Urine toxicity screen	X	X					X						
MADRS	X	X											
HAMD-17	X	X	X	X	X	X	X	X	X	X	X	X	X
CGI-S	X	X	X	X	X	X	X	X	X	X	X	X	X
CGI-I			X	X	X	X	X	X	X	X	X	X	
SF-12		X					X					X	

Visit	Double-blind Treatment Period												~30-Day Follow-Up ^a
	Screening 1	Baseline 2	3	4	5	6	7	8	9	10	11	12	
	(Day -21 to -8)	Week 0	Week 1	Week 2	Week 3	Week 4	Week 5	Week 6	Week 7	Week 8	Week 9	Week 10/ET	
Visit window (days)			±3	±3	±3	±3	±3	±3	±3	±3	±3	±3	+7
SDS		X	X	X	X	X	X	X	X	X	X	X	
DAI-10		X					X					X	
MGH-SFI		X					X					X	
KSS		X	X	X	X	X	X	X	X	X	X	X	
BIS-11		X	X		X		X	X		X		X	
SIS		X	X		X		X	X		X		X	
C-SSRS ^b	X	X	X	X	X	X	X	X	X	X	X	X	
AIMS		X	X				X	X				X	
BARS		X	X				X	X				X	
SAS		X	X				X	X				X	
Concomitant Medications	X	X	X	X	X	X	X	X	X	X	X	X	X
Assessment of adverse events	X	X	X	X	X	X	X	X	X	X	X	X	X
Dispense study drug		X	X	X	X	X	X	X	X	X	X		
Study drug accountability			X	X	X	X	X	X	X	X	X	X	

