5.3 Analysis Visit Windows

Baseline for Stage 1 of the study is defined as the last non-missing result, including results from repeated and unscheduled measurements, before first dosing in Stage 1. Baseline for subjects randomized into Stage 2 is defined as the results at Study Week 5.

Statistical Analysis Plan
2018

21 August

Efficacy, safety, and PK assessments will be summarized by analysis visit as presented in Table 2 below. For the Week 5 visit window only, the assessments collected on the date of randomization for the subjects who are randomized into Stage 2 will be selected for the analysis even if the Stage 2 randomization date is outside of the Study Day Interval, 33 - 39.

Table 2 Analysis Visit Windows

Analysis Visit	Study Visit	Target Study Day @	Study Day Interval
Baseline (Day 1 for Stage 1)	2 (Week 0)	1	≤ 1
Week 1	3 (Week 1)	8	2 – 11
Week 2	4 (Week 2)	15	12 – 18
Week 3	5 (Week 3)	22	19 – 25
Week 4	6 (Week 4)	29	26 – 32
Week 5	7 (Week 5)	36	33 – 39
Week 6	8 (Week 6)	43	40 – 46
Week 7	9 (Week 7)	50	47 – 53
Week 8	10 (Week 8)	57	54 – 60
Week 9	11 (Week 9)	64	61 – 67
Week 10	12 (Week 10)	71	68 – 78
Follow-up	~30-Day Follow-Up	101	≥79

@ Derivation of study day: study day = assessment date - first dose date + 1 if the assessment date ≥ first dose date, otherwise study day = assessment date – first dose date. Study day 1 is the day of first administration of study drug (pimavanserin or placebo).

Efficacy and safety assessments for Stages 1 and 2, when presented side by side or separately, will be summarized by analysis visit as presented in Table 3.

Table 3 Analysis Visit for Side-by-side or Separate Presentation of Stages 1 and 2

Data

Analysis Visit	Study Visit in Stage 1	Study Visit in Stage 2
Baseline (Day 1)	2 (Week 0)	7 (Week 5)
Week 1	3 (Week 1)	8 (Week 6)
Week 2	4 (Week 2)	9 (Week 7)
Week 3	5 (Week 3)	10 (Week 8)
Week 4	6 (Week 4)	11 (Week 9)
Week 5	7 (Week 5)	12 (Week 10)

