14. SAFETY ANALYSES

All safety analyses including the analysis of plasma concentration data will be performed using the actual treatment for SAS1 in Stage 1 (5 weeks) and SAS2 in Stage 2 (5 weeks). To evaluate treatment differences in 10-week safety data, unless otherwise specified, safety data from Baseline (Study Week 0) to Study Week 10 will also be summarized by treatment group for subjects in SAS1 who were not randomized to the pimavanserin group in Stage 2.

For Stage 1, Baseline is Study Week 0 and Week 5 is Study Week 5. For Stage 2, Baseline is Study Week 5 and Week 5 is Study Week 10.

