14.4 Electrocardiogram (ECG)

12-lead ECGs are collected at Screening Visit 1, Baseline (Study Week 0), Study Week 1, Study Week 5, Study Week 6, and Study Week 10/Early termination. Observed values of ECG variables (e.g., heart rate, PR interval, QRS interval, QT interval, and QTc interval) and the changes from Baseline at each assessment time point will be summarized by treatment group.

QTcF will also be categorized into the following categories (msec) and the number and percentage of subjects in each category will be summarized by treatment group at each visit and for the overall post-Baseline maximum:

- Observed: ≤450, 451 - ≤480, 481 - ≤500, and >500; >450; >480.
- Change from Baseline: ≤10, 11 – 30, 31 – 60, and >60; >30.

Statistical Analysis Plan
2018

21 August

Electrocardiogram variable values will be considered PCI if they meet the criteria listed in Table 7. The number and percentage of subjects with post-baseline PCI values will be summarized by treatment group at each post-Baseline visit and for overall post-Baseline. For the by-visit summary, the numerator for the percentage is the number of subjects with a post-Baseline PCI ECG for the given parameter, visit and treatment group, and the denominator is the number of subjects with non-missing values for the given parameter, visit and treatment group. For the overall post-Baseline summary, the numerator for the percentage is the number of subjects with at least 1 post-Baseline PCI ECG for the given parameter and treatment group, and the denominator is the number of subjects with at least 1 post-Baseline ECG value for the given parameter and treatment group. A listing of all subjects with any PCI value will be provided.

Table 7 Criteria for Potentially Clinically Important ECG Values

ECG Parameter	Unit	High PCI Criteria
QRS Interval	msec	≥120
PR Interval	msec	≥220
QTcB or QTcF	msec	>500
QTcB or QTcF: change from baseline		>60 msec

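### The exclusion 18 QTcF limit is met at Screening and Week 0 but is not re-applied at Week 5, when about 49 placebo non-responders first receive pimavanserin

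*Protocol*

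**What the plan says.** Protocol 1.3.1 states: "Pimavanserin prolongs the QT interval". It gives an average prolongation of about 5-8 ms and advises against use in known QT prolongation.

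Exclusion 18 (Protocol 4.2) applies to a subject who "Has a Screening or Baseline ECG with a QTcF >450 ms when the QRS duration is <120 ms", or above 470 ms when QRS is 120 ms or more. One repeat is allowed at either visit, in consultation with the Medical Monitor. In Table 2 (Protocol 6) the row "Inclusion/exclusion criteria" is marked at Screening and Week 0 only.

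Protocol 9.6.2.2 sets the conditions for re-randomization at Week 5: Stage 1 placebo, HAMD-17 above 14, and a reduction of less than 50% from Week 0. The IRT decides: "eligibility for randomization in the Stage 2 will be made in the double-blind manner via the IRT system". Subjects who do not qualify continue their Stage 1 treatment.

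A 12-lead ECG and the re-randomization are both listed for Week 5 (Protocol 6.5.7), but nothing links the two. Tracings are read by a qualified clinician (6.3.9), and withdrawal for an adverse event or by physician decision is possible (4.4). Neither section gives a QTc threshold. The QTcF categories in SAP 14.4 are for reporting.

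On masking, Protocol 9.6.1 says: "Investigators will be informed of the 10-week treatment period but will remain masked to the distinction between Stage 1 and Stage 2". To hide the re-randomization visit, sites enter the HAMD-17 total in the IRT at every visit.

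**The concern.** The plan tests QTcF against a numerical limit at the visit where Stage 1 subjects take their first dose, even though Screening was only 8 to 21 days earlier. Subjects who start the drug in Stage 2 rely on a qualifying ECG that is five weeks old. A newer ECG is recorded on the day the drug may start, yet its result has no stated bearing on whether it starts.

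At stake is the safety of a small group. A placebo subject whose QTcF has risen above the entry limit by Week 5 can be randomized at that visit to a drug known to lengthen it. Preventing this rests on the judgement of an investigator who has no stated threshold and does not know that a first dose may follow.

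**Working it through.** **1. The two starting points compared**

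| | Drug starts at Week 0 | Drug starts at Week 5 |
|---|---|---|
| Planned number | 47 | about 49 |
| Limit met at Screening and Week 0 | required | required |
| Further ECGs before first dose | none | Weeks 1 and 5 |
| ECG of the starting visit tied to eligibility | yes | no |
| First scheduled ECG on drug | Week 1 | Week 6 |

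The two groups differ adversely in one row: the ECG of the starting visit does not count for those who start at Week 5.

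**2. The plan's count** (Protocol 9.5: 188 randomized 1:3, 70% placebo non-response)

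- Placebo in Stage 1: 188 × 3/4 = 141.
- Non-responders: 141 × 0.70 = 98.7, or 49.4 per arm. The plan states 98 and 49, so its figure is reproduced.

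**3. Subjects affected**

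The documents give no rate r of QTcF above the limit at Week 5, so r is assumed. Expected number = 49 × r:

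- r = 0.5%: 0.25
- r = 1%: 0.49
- r = 2%: 0.98
- r = 5%: 2.45

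**4. Size of the QT shift**

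Adding the cited average of 5-8 ms to a QTcF of 451 ms gives 456-459 ms. The SAP's potentially clinically important level is above 500 ms (SAP 14.4).

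**5. Cost in power of a Week 5 ECG condition**

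Inputs from Protocol 9.5: 168 evaluable (42 and 126), w = 0.5, differences 2.2 (SD 8) and 3.2 (SD 6), two-sided 0.05. Let f be the share of non-responders who fail the condition (assumed).

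- Var1 = 64 × (1/42 + 1/126) = 2.032.
- Stage 2 per arm: n = 126 × 0.70 × (1 − f)/2.
- Var2 = 36 × 2/n = 72/n.
- Z = (0.5 × 2.2 + 0.5 × 3.2)/√(0.25 × (Var1 + Var2)) = 2.7/√(0.25 × (Var1 + Var2)).
- Power = Φ(Z − 1.96).

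| f | n per arm | Z | Power |
|---|---|---|---|
| 0 | 44.1 | 2.821 | 80.5% |
| 1% | 43.7 | 2.815 | 80.4% |
| 2% | 43.2 | 2.808 | 80.2% |
| 5% | 41.9 | 2.788 | 79.6% |

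The first row reproduces the plan's claim of at least 80%. Power reaches 80.0% at f = 3.0%.

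**The case against.** The strongest reply is that little is left uncovered. All subjects pass the limit twice, the background antidepressant dose is stable, long QT history is excluded, and Appendix A prohibits antiarrhythmics and prohibits or restricts several anti-infectives. A blinded investigator must treat every subject as possibly on drug, so a long QTcF at Week 5 would prompt caution anyway. Another ECG follows at Week 6. Week 5 laboratory, urine toxicity and C-SSRS results are not re-randomization conditions either. Most of this stands and limits the weight of the point. It does not close the gap. No QTc threshold or action is stated after Week 0. Only the IRT can know who is about to be re-randomized. A Week 6 finding comes after about a week of dosing with a drug whose half-life is about 57 hours, and about 200 hours for its active metabolite (Protocol 1.1.1). QT also differs from the other Week 5 assessments in that the protocol names prolongation as a known effect of the drug.

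A second reply is that a placebo subject at 455 ms would be kept off the drug while a Stage 1 pimavanserin subject at 455 ms continues. That is coherent: an entry limit governs starting a drug, a stopping rule governs continuing it, and only the first is at issue.

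Two stronger readings are tempting:

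- From 49/(47 + 49) = 51%, a reader might infer that half of first exposures occur with no QTcF limit. They do not: all 96 met the limit at Screening and Week 0, and the 49 also have a Week 1 ECG.
- A reader might infer an eligibility rule from the SAP's definition of Baseline. SAP 5.3 says "Baseline for subjects randomized into Stage 2 is defined as the results at Study Week 5"; SAP 14 repeats for safety data "For Stage 2, Baseline is Study Week 5 and Week 5 is Study Week 10"; and SAP 14.4 adds that "the changes from Baseline at each assessment time point will be summarized by treatment group". These fix the reference for change scores. They neither extend exclusion 18 to Week 5 nor show that it should apply. Protocol 3.2 likewise defines Baseline by stage only for the endpoint wording.

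**Conclusion.** The point holds in a limited form. The exclusion 18 limit is not re-applied at Week 5, when about 49 subjects first receive pimavanserin, although an ECG is taken at that visit. What is uncovered is a rise in QTcF above the limit during five weeks on placebo, partly mitigated by clinician review and discretionary withdrawal. At an assumed 0.5% to 5% it concerns about 0.2 to 2.5 subjects. That range is an assumption, because the documents give no rate.

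A reader might go further and infer harm, or an error in the sample size or analysis. The documents show neither: the count is of threshold crossings, the average shift stays well below 500 ms, and the plan's power figure is reproduced. A separate IRT manual, mentioned in Protocol 9.6.3, was not available, so a rule there cannot be ruled out; the protocol and SAP state none. Severity is low to moderate, and the case for acting rests largely on how little the remedy costs.

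**What to change.** In Protocol 9.6.2.2, add that the Week 5 ECG must meet the exclusion 18 QTcF limit for re-randomization. To keep Week 5 from standing out, use the same procedure at every post-baseline ECG visit (Weeks 1, 5, 6 and 10): the site reads the ECG before the IRT transaction, may repeat it once, and enters whether the ECG condition is met, yes or no. The IRT uses only the Week 5 entry, and only for placebo non-responders. Those who fail stay on placebo under the existing rule. Clinician discretion on any post-baseline QTcF is unchanged.

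Text to amend:

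- the synopsis;
- Protocol 9.2, which equates re-randomized subjects with placebo non-responders;
- Protocol 9.4.1, whose list of subjects not eligible for re-randomization must add non-responders who fail the ECG condition;
- Protocol 9.6.1, on IRT entries;
- footnote c of Protocol Table 2 and SAP Table 1, which allows a repeat only at Screening or Baseline;
- the single-recording wording in Protocol 6.5.3, 6.5.7, 6.5.8 and 6.5.12;
- SAP 3.1 and 3.3.2.

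The Stage 2 analysis sets in SAP 4 already require randomization into Stage 2 and need no change.

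The cost is one IRT field, a short amendment and the need to read the ECG within the visit; at Week 0 the ECG, randomization and first dose already share a visit. No scheduled ECG is added. The Stage 2 population narrows slightly. Power stays at or above 80% up to a 3.0% loss and is 79.6% at 5%, if the assumed effects and SDs are unchanged. No added enrolment is needed. A QTc stopping rule for all subjects would be a separate matter, and the documents give no threshold for one.
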